We will assess the feasibility, acceptability, and pre-to-post intervention improvement in outcome variables using a single-arm pilot study (N=30). Standardized self-report assessment measures will be administered at baseline, immediately post-intervention, and 1 month follow-up. Participants can complete assessments via hard copy or online via RedCap. All participants will be offered participation in an exit interview to inform DBT-MLC refinement. If necessary and appropriate, patient participants in Phase II of the study may be provided with a device (e.g., tablet computer) to participate in the pilot intervention program. A data plan will be provided if necessary. These will be set with restrictions. Participants will return tablet computers following completion of study activities.

Study personnel will be trained in procedures related to delivering DBT-MLC. [name] will attend formal trainings in delivering DBT skills training as part of the fellowship project. She will create a standard operating procedure manual for the delivery of DBT-MLC. Study interventionists will thoroughly review the treatment manual and rehearse intervention delivery by role playing skills training sessions.

• List inclusion/exclusion criteria and how subjects will be identified.

Eligibility criteria for patients. Eligibility criteria for patients were determined in consultation with mentor and thoracic oncologist, [name], MD, and based on previous psychosocial studies in advanced lung cancer.

Eligibility criteria for patients included in Phase I and Phase II include:

- 1) be diagnosed with metastatic (AJCC stage IV) non-small cell lung cancer,
- 2) be undergoing systemic treatment (chemotherapy, targeted therapy, and/or immunotherapy) for lung cancer at DCI.
- 3) score \geq 3 on the National Comprehensive Cancer Network Distress Thermometer for distress over the past week (Range: 0-10),
- 4) be > 18 years of age,
- 5) be able to understand, speak, and read English, and
- 6) be able to provide informed consent.

Exclusion criteria for patients include:

- 1) reported or suspected cognitive impairment subsequently informed by a Montreal Cognitive Assessment (MOCA) of <26;
- 2) presence of untreated serious mental illness (e.g., schizophrenia) indicated by the medical chart, treating oncologist, or other medical provider; or
- 3) expected survival of 4 months or less.

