• If not already presented in #4 above, describe study-related treatment or use of an investigational drug or biologic (with dosages), or device, or use of another form of intervention (i.e., either physical procedures or manipulation of the subject or the subject's environment) for research purposes.

The primary (psychological distress) and secondary outcome measures (fatigue, dyspnea, pain, emotion regulation, tolerance of uncertainty, DBT skills use) will be collected at all three assessment time points. We selected brief measures to reduce patient burden. It is estimated that assessments will take approximately 20-30 minutes to complete.

- a. Sociodemographic, clinical, and lifestyle variables. Baseline assessment will include relevant sociod emographic variables (e.g., age, race, ethnicity, employment, education). Clinical information (e.g., date of cancer diagnosis, date(s) and type(s) of treatment) will be collected via medical record review. Participants will self-report lifestyle characteristics (e.g., cigarette smoking, alcohol consumption).
- **b. Feasibility.** Treatment feasibility will be assessed through analysis of study process data, including study accrual (goal met in the allotted time frame), session attendance (\geq 80%), and treatment attrition (\leq 25%). Reasons for missed sessions and study discontinuation will be collected.
- c. Acceptability. Acceptability will be assessed post-intervention using the 8-item Client Satisfaction Questionnaire (CSQ). The scale includes eight items assessing participants' level of satisfaction with treatment, with response options ranging from 1 (quite dissatisfied) to 4 (very satisfied). Acceptability will be demonstrated by 80% of participants reporting intervention satisfaction on the CSQ. Intervention engagement will be assessed on an ongoing basis and recorded in RedCap (i.e., homework completion).

d. Pre- to Post-Intervention Outcomes.

Psychological Distress. Distress will be measured using the PROMIS Depression (8 items) and Anxiety (8 items) Short Form Scales. Participants are asked to rate how frequently they experienced each symptom over the past 7 days on a 5-point scale ranging from 1 (never) to 5 (always), with higher scores indicating greater distress (i.e., more depression or anxiety). PROMIS measures of distress have demonstrated reliability and validity in cancer samples as well as sensitivity to change in patients participating in psychological interventions.

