Data management and attrition. Participant identifying information will be stored in a secure study database. It will not be stored with questionnaire data to protect patient confidentiality. We anticipate approximately 26% attrition from baseline to immediately post-intervention based on previous supportive care interventions in people with cancer. ⁹⁰ Therefore, we will recruit approximately 38 participants to obtain full data from 30 participants. Reasons for withdrawal will be collected when possible. Data will be checked on an ongoing basis for completeness. If data are determined to be missing systematically, we will consider statistical approaches to manage data missingness (i.e., data imputation methods). [name] will work with statistical experts to determine the most appropriate methods for handling missing data. **ii.**

Statistical Power. Phase 1 will include 4-6 focus groups of approximately 5 patient stakeholders each (N=20), and individual interviews with thoracic oncology providers (N=6) and palliative care, survivorship and behavioral symptom management experts (N=6). Assuming the same potential rate of attrition for focus groups due to scheduling conflicts, illness, etc., we will recruit up to 26 participants to get focus group data from 20 participants (assuming 26% attrition). For Phase 2, we will recruit up to 38 participants to get complete data on approximately 30 participants (assuming 26% attrition). These numbers were calculated based off of relevant literature and work that has been previously successfully completed in this setting. 64,90 Literature suggests that 2-3 focus groups are necessary to reveal 80% of qualitative themes.

Analytic Plan.

Aim 1: Adapt Intervention. In-depth interviews and focus groups will be transcribed verbatim using QSR NVivo software. Data analyses will be based on a grounded theory approach, which has been used in the development of other psychosocial interventions for patients with cancer. ⁹² [name] will complete several workshops on analyzing qualitative data (see Training Plan). Additionally, the PI and members of the mentoring team have experience with qualitative data analyses. [name] is a member of the Cancer Control and Population Sciences Program at DUMC, which has a shared resource of qualitative analytic experts. Experts will be consulted as necessary to ensure appropriate handling and conducting of qualitative analyses.

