iv. Aim 2: Test and Refine Intervention. Descriptive statistics (frequencies, mean, median, standard deviation) will be used to examine feasibility (i.e., \geq 80% of sessions completed, attrition \leq 25%) and acceptability (i.e., \geq 80% participants report satisfaction on CSQ). Paired sample t-tests will be run to quantify the degree of change over time for the primary and secondary intervention outcomes. Effect sizes will be computed using Cohen's d. Unconditional latent growth models will be used to assess main time effects across baseline, immediately post-treatment and 1 month post-treatment. Time will be coded as the number of weeks since the baseline assessment. Control variables and their interactions with time will be included in conditional models. Analyses will be conducted using an intent-to-treat approach to include all available data (N=up to 38). Exit interviews will be coded and analyzed using methods similar to those described under Aim 1. Themes and feedback that are uncovered through exit interviews will be used to inform intervention refinement.

Data & Safety Monitoring

• Summarize safety concerns, and describe the methods to monitor research subjects and their data to ensure their safety, including who will monitor the data, and the frequency of such monitoring. If a data monitoring committee will be used, describe its operation, including stopping rules and frequency of review, and if it is independent of the sponsor (per 45 CFR 46.111(a) (6)).

The proposed study carries minimal risk. The protocol does not use an investigational drug, procedure, or device. Data obtained from participants will include information from medical chart review, stakeholder interviews and focus groups, and self-report inventories. The study team considers the management of participant information and data as a key priority. Best practices for confidentiality and data management will be observed. Two password protected databases will be used for this study to ensure confidentiality.

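### At the plan's own 26% attrition, 38 Phase 2 recruits are expected to give about 28 participants with post-intervention data, not the stated 30

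*Combined protocol and SAP*

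**What the plan says.** The Phase 2 numbers appear in three parts of the combined protocol and SAP.

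- **Data Analysis & Statistical Considerations, data management and attrition.** The attrition assumption is "We anticipate approximately 26% attrition from baseline to immediately post-intervention based on previous supportive care interventions in people with cancer". The recruitment figure is then presented as its consequence: "Therefore, we will recruit approximately 38 participants to obtain full data from 30 participants".
- **Same section, Statistical Power.** The claim is repeated with the rate attached: "we will recruit up to 38 participants to get complete data on approximately 30 participants (assuming 26% attrition". The numbers are attributed to literature and to earlier work in the same setting. No power, precision or effect-size calculation is given for Phase 2.
- **Design & Procedures, Phase 2.** Outcomes will be assessed "using a single-arm pilot study (N=30"), and the schedule has three time points: "Standardized self-report assessment measures will be administered at baseline, immediately post-intervention, and 1 month follow-up".
- **Analytic Plan, Aim 2.** "Paired sample t-tests will be run to quantify the degree of change over time for the primary and secondary intervention outcomes". The same paragraph adds: "Analyses will be conducted using an intent-to-treat approach to include all available data (N=up to 38").

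Acceptability also depends on post-intervention data. Under Study Interventions, "Acceptability will be assessed post-intervention using the 8-item Client Satisfaction Questionnaire (CSQ").

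**The concern.** The plan presents 30 as the number that follows from recruiting 38 and losing 26%. It does not follow. As the documents give no other quantitative basis for the Phase 2 size, this calculation is the main justification a reader has, and it fails on its own inputs.

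What is at stake is the number of pre-post pairs a reader should expect. The paired t-tests and Cohen's d need a post-intervention value, and so does the satisfaction rate. Feasibility rates measured on everyone enrolled are not affected.

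Two features make the number harder to read. The design section calls the pilot N=30 while the analysis paragraph works with up to 38, so it is unclear on the page whether 30 means enrolled or completing. And the 26% stops at the immediate post-intervention assessment although a 1-month assessment follows. The plan does not say whether full or complete data includes that last visit.

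**Working it through.** **Inputs, all from the plan.** Recruits: 38. Attrition to post-intervention: d = 0.26. Target with data: 30.

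**Reproducing the stated 38.**

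- Dividing by the retained fraction: 30/(1 − 0.26) = 30/0.74 = 40.5, so 41. This does not give 38.
- Multiplying by one plus the attrition: 30 × 1.26 = 37.8, so 38. This does.

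The second form is a common slip, because 26% is lost from those recruited and not from those who finish. The plan does not show its formula, so this origin is an inference.

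**What 38 recruits deliver at 26%.**

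- Expected with post-intervention data: 38 × 0.74 = 28.1.
- Attrition implied by 30 from 38: 8/38 = 21.1%.
- Check on 41 recruits: 41 × 0.74 = 30.3.

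**Does rounding of the 26% explain it?** No. At 25.5% the expected number is 38 × 0.745 = 28.3, and at 26.5% it is 38 × 0.735 = 27.9. Even at 25%, the limit in the plan's own feasibility criterion, it is 38 × 0.75 = 28.5.

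**Chance of reaching 30.** If each recruit independently has a 74% chance of completing (an assumption), the exact binomial probability of at least 30 completers is 0.31 with 38 recruits and 0.63 with 41.

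**Effect on precision and detectable change.** The plan gives no alpha, power or effect size, so the following are illustrations with assumed inputs.

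| Quantity | Assumption | n = 28 | n = 30 |
|---|---|---|---|
| 95% half-width, satisfaction rate, 1.96 × √(0.8 × 0.2/n) | 80% satisfied, normal approximation | 14.8 points | 14.3 points |
| Detectable paired d (noncentral t) | two-sided alpha 0.05, 80% power | 0.55 | 0.53 |

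**Loss after post-intervention.** The documents give no figure, so none is computed. If complete data includes the 1-month assessment, the expected number is at or below about 28.

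**Phase 1, side note.** The focus-group figure has the same form: 26 recruits at 26% give 26 × 0.74 = 19.2 against a stated 20, a gap of less than one participant.

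**The case against.** The best defence is that the plan speaks in approximations and that nothing is computed from the 30. The attrition rate and one of the two recruitment statements are given as approximate, and the other statement hedges the 30. The gap is 1.9 participants, about 6%. A 0.31 chance of reaching 30 makes the figure optimistic but not out of reach. The intent-to-treat approach uses all available data from up to 38 participants, and imputation may be considered if data are missing systematically.

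Much of this stands as to weight, and it keeps the point minor. It does not remove the inconsistency. One of the two statements gives 30 with no hedge, rounding does not close the gap, and both statements tie the number to the 26%. Including all available data does not create a post-intervention value for a paired test or a satisfaction rating, and imputation is only a possibility in the plan.

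It can also be said that the choice of remedy belongs to the sponsor, who could recruit 41 or justify attrition near 21%. That is fair, but both cost more than rewording: one adds participants, the other needs evidence the plan does not contain.

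A last point is that writing down 28 expected completers exposes a conflict, since the anticipated 26% already misses the 25% attrition criterion if both are counted the same way. That conflict is in the plan as it stands, and the rewording does not create it. Likewise, the feasibility criterion refers to an accrual goal without a number, so N=30 might be read as that goal. The attrition text, however, already makes 38 the recruitment figure and 30 the completer figure.

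**Conclusion.** The concern holds, as a minor arithmetic error. Taking the plan's 38 recruits and 26% attrition at face value, the expected number with post-intervention data is 28.1, about two fewer than stated. The size of the discrepancy rests on no outside assumption; only the completion probabilities and the precision figures do. The half-width changes by about 0.5 percentage points and the detectable d by about 0.02, and neither would alter the conclusion of this single-arm pilot. The benefit of correcting it is that readers do not take 30 as the expected number of pre-post pairs.

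**What to change.** Make these wording changes:

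1. In the data management and attrition paragraph and again under Statistical Power, replace the 38-to-30 statements with: *We will recruit up to 38 participants; at 26% attrition about 28 are expected to have post-intervention data. The 26% does not cover further loss by the 1-month assessment.*
2. In Design & Procedures, Phase 2, replace the N=30 with: *up to 38 enrolled; about 28 expected with post-intervention data*. This agrees with the up to 38 in the Analytic Plan.
3. If the Phase 1 sentence is edited at the same time, state about 19 from 26.

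The cost is text only. No participants are added and neither the design nor the analysis changes; the stated completer number falls from 30 to about 28. Should the sponsor prefer to keep 30 as a firm target, the consistent alternatives are to recruit 41 or to justify attrition of about 21%.

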All participants in the study will continue their medical care during the course of the study and will be informed that choosing to participate in the study will in no way impact the treatment they receive at the DCI and DUMC. All participants will continue to be monitored by their physicians at the DCI throughout the course of the study. If a health concern is identified during contact with study staff, the patients' treating oncologist will be contacted, and appropriate referrals for medical treatment will be provided to patients. [name] (PI), [name] (F32-awardee and study coordinator) will continuously monitor and tabulate adverse events. An adverse event is any untoward medical event occurring during the clinical evaluation, which is causally related to the study protocol. A serious adverse event is defined as any event which results in death, is immediately life threatening, results in persistent or significant disability/incapacity, results in patient hospitalization, or is serious for any other reason representing significant hazard. For each event, the investigator will provide the onset, duration, intensity, treatment required, outcome, and action taken. Given the study population (i.e., patients with metastatic lung cancer), it is possible that some participants will be hospitalized and/or die while enrolled. Adverse events due to advancement of lung cancer will not be reported, as these are unrelated to participation in this supportive behavioral intervention. If an unexpected frequency of Grade III or IV events occur, depending on their nature, action appropriate to the nature and frequency of these adverse events will be taken. This may require a protocol amendment, dose de-escalation, or potentially closure of the study. [name] (PI), [name] (F32awardee and study coordinator) will also continuously monitor the conduct, data, and safety of this study to ensure that:

- Risk/benefit ratio is not altered to the detriment of the subjects;
- Appropriate internal monitoring of AEs and outcomes is done;
- Over-accrual does not occur;
- Under-accrual is addressed with appropriate amendments or actions;
- Data are being appropriately collected in a reasonably timely manner.

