Likewise, [name] (PI) and [name] (F32-awardee and study coordinator) will appoint two data safety officers. One data safety officer will be a MD within the Duke University Medical Center (DUMC) who is not associated with this study. The appointed MD officer will have experience with clinical research and trials, and will have a thorough understanding of adverse events. The other safety data officer will be a DUMC senior investigator who has expertise in psychological treatment and behavioral symptom management, and will have an annual responsibility to evaluate our current methods of assessment and intervention to identify any problems. All adverse events will be reported to the data safety officers in real time.

This study will also be monitored institutionally by the Duke Cancer Institute (DCI). DCI Protocol Review and Monitoring systems (PRMS) review of this protocol begins with an initial review by the Cancer Protocol Committee (CPC). CPC new protocol review focuses on scientific relevance, study design, adequacy of biostatistical input, protocol prioritization, feasibility of completing the study within a reasonable time frame and risk assessment of the trial. The PI will abide by CPC assessment of the level of risk, which will determine the intensity of subsequent DCI monitoring. CPC also conducts annual scientific progress reviews on protocols that are open to enrollment and focus on protocol prioritization, accrual and scientific progress. These reviews are conducted at the time of IRB annual renewals and documentation of all CPC reviews will be maintained in eIRB/iRIS systems.

A determination for the degree of monitoring conducted by the DCI monitoring team is made at the time of initial CPC approval to commensurate with the type and level of intervention, phase, endpoints, degree of risk, size and complexity of the protocol. A formal, independent monitoring will be conducted by the DCI monitoring team according to the risk level and monitoring plan assigned by the CPC until the study is closed to enrollment or subjects are no longer receiving study drug or other interventions that are more

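### The adverse event definition presupposes causality and conflicts with the serious-event and progression sentences, so an unrecorded attribution decides which events the plan clearly sends to the safety officers

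*Combined protocol and SAP*

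**What the plan says.** All the relevant text is in the Data & Safety Monitoring section of the combined protocol and SAP.

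- Definition of an adverse event: "An adverse event is any untoward medical event occurring during the clinical evaluation, which is causally related to the study protocol".
- Definition of a serious event: "A serious adverse event is defined as any event which results in death, is immediately life threatening", followed by further outcome criteria that include hospitalization. No causal condition is attached.
- Exclusion: "Adverse events due to advancement of lung cancer will not be reported, as these are unrelated to participation in this supportive behavioral intervention".
- Who tabulates: the PI and the awardee/study coordinator "will continuously monitor and tabulate adverse events".
- What is recorded: "For each event, the investigator will provide the onset, duration, intensity, treatment required, outcome, and action taken".
- What the two safety officers receive: "All adverse events will be reported to the data safety officers in real time".
- Who the officers are: "One data safety officer will be a MD within the Duke University Medical Center (DUMC) who is not associated with this study"; "The other safety data officer will be a DUMC senior investigator who has expertise in psychological treatment and behavioral symptom management". Only the first is stated to be outside the study.

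The same section accepts that some participants may be hospitalized or die while enrolled. It also says that an unexpected frequency of Grade III or IV events will prompt action, up to closing the study.

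**The concern.** Safety reporting normally separates two questions: did something untoward happen, and was the study the cause? Here the second question is folded into the first. The study team has to settle relatedness before an event counts as an adverse event, and the promise to the safety officers covers adverse events only.

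This matters more than usual for two reasons. The pilot has a single arm, so no comparison group can show an excess of events. The participants have stage IV lung cancer, are on systemic treatment and are selected for distress, so there is nearly always a plausible disease-related explanation for a deterioration or an admission. If that explanation is accepted without being recorded, an outside reader cannot later see that a judgement was made, or by whom.

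**Working it through.** No arithmetic applies. The check is to take the sentences together and follow each kind of event through them.

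| Event as judged by the study team | Meets the adverse event definition? | Meets the serious-event sentence? | Caught by the progression exclusion? | Route to the safety officers |
|---|---|---|---|---|
| Related to the protocol | Yes | If an outcome criterion is met | No | Real-time report |
| Non-serious, unrelated, not progression | No | No | No | None described |
| Non-serious, attributed to progression | No, though the exclusion calls it an adverse event | No | Yes | Expressly not reported |
| Serious, attributed to progression | No, as above | Yes | Yes | Expressly not reported |
| Serious, unrelated, not progression | No | Yes | No | Unclear |

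Three results follow.

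1. **The sentences conflict.** If an adverse event must be related to the protocol, an unrelated adverse event cannot exist, and the progression exclusion has nothing to exclude. If serious events need no causal link, they are not a subset of adverse events. Staff cannot tell which reading governs. The last row shows the practical effect: an admission put down to the toxicity of systemic treatment, for example, meets the serious-event wording, fails the adverse event definition and is not excluded. The plan describes no separate reporting route for serious events, so its destination is undefined.

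2. **Attribution leaves no trace.** The recorded fields are onset, duration, intensity, treatment, outcome and action. None holds the relatedness judgement, yet that judgement decides which row of the table applies.

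3. **No one is described as reviewing attribution.** The officers receive adverse events. The institutional monitoring team reviews whether event monitoring and reporting are appropriate, but a monitor working from this definition could find an unreported unrelated event compliant.

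The Grade III/IV sentence inherits the problem. It refers back to the events it counts as adverse events, so on the literal definition it counts only events already judged related. On the broader usage in the exclusion sentence it could count more. The text does not say which.

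**The case against.** The strongest reply is that the definition is loose drafting in a minimal-risk behavioural pilot, and that the documents provide several safeguards which do not depend on it. Much of this stands.

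- A reader might infer that events judged unrelated are never logged. The documents do not say so. Progression events are said to be unreported, not unrecorded. The sentence listing the event fields is not limited to related events. Reasons for missed sessions, discontinuation and withdrawal are also to be collected (Study Interventions, Feasibility; Data management and attrition). However, none of those records is directed to the safety officers.
- A reader might infer that worsening depression or suicidality would go unseen. That is not supported. Depression and anxiety are the primary outcome and are measured at three time points. Suicidality falls under a separate prevention plan, held in a document not available here. Licensed psychologists supervise contacts and review session recordings.
- A reader might infer that review by the safety officers is the only safeguard, or that both officers are independent. Neither holds. Treating physicians continue to monitor participants, one officer evaluates the study's methods annually, and the institutional team reports to a Safety Oversight Committee. Only the MD officer is stated to be unassociated with the study.
- The progression exclusion would be redundant under a literal definition, which suggests that the authors did not mean the definition literally. That is fair, but it supports rewriting the sentence.
- Logging every untoward occurrence in stage IV patients on systemic treatment takes effort, and counting all of them towards the Grade III/IV sentence would make it non-specific in a study without a control arm. This also stands. The remedy should not redefine that sentence, which can lead to study closure.

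What the reply does not meet is the core point: none of these safeguards is described as a review of whether an event was correctly attributed.

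**Conclusion.** The point holds as a conflict between three sentences and a resulting gap in safety reporting. Non-serious events judged unrelated have no planned tabulation or report; events attributed to progression are expressly not reported, whatever their seriousness; other serious events judged unrelated have no clear route.

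Its size cannot be given as a number. The documents contain no event rates, so only the population exposed to the gap is known: up to 38 pilot participants. It is tempting to say that a report of no adverse events would follow from the definition alone, particularly as the Risks text anticipates none. The documents do not support that, because it is unknown how many events would be filtered or how staff would apply the wording.

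The conclusion assumes that the definition is read as written and that no document outside this one supplies a further reporting route or attribution record. The wording conflict is certain; its effect in practice is not. Safety is not an endpoint, so no feasibility, acceptability or outcome conclusion changes. The text should still be corrected, because the gap concerns oversight of a seriously ill population and is inexpensive to close.

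**What to change.** In Data & Safety Monitoring:

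1. Reconcile the three sentences. Define an adverse event by its occurrence, regardless of cause, and make serious adverse events a subset of that definition.
2. Add a relatedness field to those already recorded, with the categories study protocol, disease or its treatment, and other.
3. Keep progression events out of real-time reporting, but give the MD safety officer a periodic cumulative listing of serious events and progression-attributed events, each with its recorded attribution. Because the definition widens, adjust the real-time reporting sentence to say which adverse events it covers.
4. Have the sponsor state which events the existing Grade III/IV sentence counts. The choice is the sponsor's; the need is only that the text be unambiguous.

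The cost is revised wording, one more field, a periodic listing and a somewhat longer event log for up to 38 participants. Some extra effort goes into recording ordinary disease and treatment events. No new staff are needed, since both officers are already planned.
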